4.1.2 On Study Data Collection

We will also document bead visibility data during embolization. This information will be collected using a qualitative particle visibility scale by applying a 3-point scale: 0, definitely not visible; 1, probably visible; and 2, definitely visible [21].

Intra-procedural, post treatment, and follow up images will all be saved and stored in PACS. Patient images will be anonymized prior to transfer to a secure work station for analysis. CRF's and non-image data will be stored in the DRD shared drive which has limited access. The DRD shared drive is backed up and managed by the NIH DCRI in keeping with the protection and confidentiality guideline of the Privacy Act of 1974.

Any grade 3 events and higher occurring up to 72 hours post treatment (either with combined RFA and TAE or with TAE alone) will be collected and recorded in the study database as adverse events, except those listed in the Exclusions to Adverse Event Data Collection section (see Section 4.1.3). Grade 2 events will be collected and recorded if not resolved before the patient is considered off treatment (72 hours post treatment). Grade 1 events will not be collected or reported.

Abbreviated Title: RFA + TACE with RO Beads

Version Date: 04/13/2018

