4.1.3 Exclusions to Adverse Event Data Collection

The following adverse events are expected events from the procedure and study device and will not be collected unless the nature, severity, and frequency are deemed by the PI as unexpected for this patient population.

Anticipated adverse events related to TAE:

- Fever
- Right upper quadrant pain
- Acute cholecystitis
- Acute pancreatitis or elevation of amylase and lipase
- Nausea
- Vomiting
- Fatigue
- Elevated white blood cell count
- Elevated liver enzymes
- Bleeding
- Groin hematoma
- Arterial dissection
- Portal vein thrombosis
- Pleural effusions
- Aspiration pneumonia from intubation
-

Anticipated adverse events related to ablation procedure:*

- Pain at the site of ablation needle insertion
- Muscle ache
- Fever
- Fatigue
- Nausea
- Vomiting
- Elevated liver function tests
- Hyponatremia following hydro-dissection
- Thrombocytopenia and anemia post-RFA
- Pleural effusions
- Aspiration pneumonia from intubation
- Bleeding

*If ablation is given

Anticipated adverse events related to LC LUMI beads (will collect if grade 3 or above):

- Allergic reaction to LC LUMI beads

Abbreviated Title: RFA + TACE with RO Beads

Version Date: 04/13/2018

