4.3 RESPONSE CRITERIA

4.3.1 Definitions

- Evaluable for bead visibility: All patient imaging will be evaluated for the visibility of the LC LUMI beads using a 3 point scale: 0, definitely not visible; 1, probably visible; and 2, definitely visible as defined the treating interventional radiologists. Other characteristics may be noted such as the radiopacity of the beads, visibility of the beads in the tumor, overall location of beads in relation to the tumor or targeted site.
- Evaluable for toxicity: All patients will be evaluable for toxicity from the time of their treatment with LC LUMI radiopaque beads up to 72 hours post completion of treatment. Grade 3 or greater adverse events, including allergic reactions, collected during this time period, will be followed until resolution. Expected or anticipated adverse events from the research or the study device will not be collected. See Section **4.1.3** for details.
- Evaluable for imaging characteristics: Only those patients who are eligible for the study, have received at least one treatment of TAE, and have had their disease re-evaluated per standard of care imaging will be considered evaluable.

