		
observation period)
 
 • Abdominal visceral injury (from non-target embolization, 1-2 weeks following embolization): 		
of misembolization.
 
Patient are admitted to the inpatient hospital ward during the immediate post-operative period and monitored.
 
Post-operative changes in patient comfort vital signs or diagnostics such as liver enzymes will prompt further evaluation.

2	LC Lumi beads	Allergic Response	The preclinical experience does not raise concerns that the radiopaque LC beads produces any known acute allergic response (see Investigator's Brochure).	Patient with known allergy to LC beads or its components will be excluded from the study
3	LC Lumi beads	Endotoxin adverse reaction	The preclinical experience does not raise concerns that the radiopaque LC beads produces any known acute endotoxin response (see Investigator's Brochure).	
Labeled non-pyrogenic Endotoxin testing in animal models proved no change in temperature during an observation period following injection of extracted LC bead LUMI.
 
Acutely febrile patients will be excluded from the procedure as is standard of care

4	LC Bead LUMITM Bead	Genotoxicity, Carcinogenicity, reproductive toxicity	The preclinical experience does not raise concerns that the radiopaque LC beads produces any known genotoxicity, carcinogenotoxic or reproductive toxic adverse events (see Appendix C, Section 0)	Patients who are of reproductive age will be counseled on use of adequate birth control. All women who are of reproductive age and are not sterile or post-menopausal will be tested for pregnancy prior to all imaging.
5	LC Bead LUMITM beads	Systemic or local toxicity	The preclinical experience does not raise concerns that the radiopaque LC beads produces any known acute systemic or local adverse response (see Appendix C, Section 0)	Patient are admitted to the inpatient hospital ward during the immediate post-operative period and monitored. Post-operative changes in patient comfort, physical exam, vital signs or diagnostics such as liver enzymes will prompt further evaluation with imaging and immediate treatment.

Abbreviated Title: RFA + TACE with RO Beads

Version Date: 04/13/2018

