10.1.2 Preparation of LC Bead LUMI™

1. During preparation of LC Bead LUMI™, use controlled aseptic conditions.
2. Remove the plastic color coded flip cap from LC Bead LUMI™ vial but do not remove the metal ring around the stopper. With the spike of the ViaLok™ Vented Access Device centered to the rubber stopper of the vial, attach the device until the retention tabs snap on the LC Bead LUMI™ vial.

Abbreviated Title: RFA + TACE with RO Beads

Version Date: 04/13/2018

Note: The ViaLok™ Vented Access Device is not for direct infusion and should only be used for transfer of the beads into a syringe. The access device size corresponds to vial diameter and is intended for use with ISO-594 compatible mating luers. LC Bead LUMI™ has only been tested in conjunction with ViaLok™ Vented Access Device.

3. Remove and discard luer cap from the access device.

Note: To minimize risk of potential contamination, the ViaLok™ Vented Access Device protective cap shall remain attached to luer until accessed by the mating luer device.

4. Attach a 10ml syringe to the luer lock of the ViaLok™ Vented Access Device.

5. Invert vial and suspend the beads in solution by agitating in a swirling motion whilst drawing the LC Bead LUMI™ into the syringe.

6. Once all the solution is transferred discontinue the agitation and maintain the vial in the inverted position to allow the beads to settle in the syringe. Return only the clear solution to the vial and repeat previous step to recover remaining beads from the vial. This process may be repeated twice if required.

Note: Small traces of LC Bead LUMI™ may be retained in the vial.

7. Once LC Bead LUMI™ has settled at the bottom of the syringe; disconnect the syringe from the ViaLok™ Vented Access Device. Expel all packing solution to waste or suitable container, leaving only LC Bead LUMI™ within the syringe

8. LC Bead LUMI™ should be prepared for administration using 100% non-ionic contrast agent to obtain an optimum suspension. Please refer to Table 2 of the IFU (Appendix C, Section 0) for recommended contrast agents.

9. Attach a connector to the syringe containing LC Bead LUMI™. Using a 20ml syringe take up 20ml of contrast agent and connect to the 10 ml syringe containing the LC Bead LUMI™.

10. Gently mix LC Bead LUMI™ and contrast agent between syringes through the connector, until a homogenous suspension is achieved.

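### By default, a grade 2 allergic reaction still open at 72 hours is recorded if blamed on contrast but not if blamed on the bead, although the two are injected as one mixture

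*Combined protocol and SAP*

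**What the plan says.** Four places in the combined protocol and SAP bear on whether an allergic reaction is recorded.

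- **Section 4.1.2 (general rule).** Events of grade 3 or higher up to 72 hours after treatment are recorded, "except those listed in the Exclusions to Adverse Event Data Collection section (see Section 4.1.3"). The next sentence sets the grade 2 rule: "Grade 2 events will be collected and recorded if not resolved before the patient is considered off treatment (72 hours post treatment"). Grade 1 events are not collected.
- **Section 4.1.3 (exclusions).** Its listed events "will not be collected unless the nature, severity, and frequency are deemed by the PI as unexpected for this patient population". There is one list for TAE and one for ablation. The third heading reads "Anticipated adverse events related to LC LUMI beads (will collect if grade 3 or above"), and its only entry is "Allergic reaction to LC LUMI beads".
- **Section 4.3.1 (toxicity evaluability).** It says that grade 3 or greater events, allergic reactions among them, are followed to resolution. It then says "Expected or anticipated adverse events from the research or the study device will not be collected" and refers the reader to 4.1.3.
- **Section 9.5 (risk table).** Allergy to intravenous contrast is a named harm of the procedure. It is in none of the three 4.1.3 lists, so the general rule in 4.1.2 governs it.

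On how the product is given, Section 10.1 says that the beads are mixed with non-ionic contrast, and Section 10.1.2 that they "should be prepared for administration using 100% non-ionic contrast agent to obtain an optimum suspension". The instructions for use in Appendix C list allergy to contrast and allergy to the beads as a single potential complication.

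**The concern.** Whether a safety event is recorded should not depend on which of two agents, injected together, the investigator blames. Section 4.1.4 has the investigator judge causality for adverse events that have been reported. The bead entry in 4.1.3 reverses that order: at grade 2, a causal judgement comes first and determines whether there is a record. A reaction attributed to the bead then leaves nothing in the study database that could later be reviewed or reclassified.

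The affected category matters for this device. Section 9.5 describes the study bead as essentially the standard bead with iodine attached, and its reassurance on allergy is preclinical: "The preclinical experience does not raise concerns that the radiopaque LC beads produces any known acute allergic response". Section 5.4.1 bases decisions on continued enrolment on toxicity data from earlier patients. A final statement that no allergic reactions to the beads occurred could be read as covering all grades when only grade 3 and above had been captured.

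**Working it through.** No sample size, power or error rate enters this point, so the check is to apply the recording rules side by side. The inputs are the grade 2, grade 3+ and grade 1 sentences of 4.1.2, the bead heading of 4.1.3, and the absence of contrast allergy from 4.1.3. The table assumes a non-serious reaction within the 72-hour window and no override by the principal investigator.

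| Allergic reaction | Blamed on contrast | Blamed on bead, 4.1.3 governs | Blamed on bead, 4.1.2 grade 2 sentence read literally |
|---|---|---|---|
| Grade 1 | not recorded | not recorded | not recorded |
| Grade 2, resolved by 72 hours | not recorded | not recorded | not recorded |
| Grade 2, open at 72 hours | **recorded** | **not recorded** | recorded by 4.1.2, excluded by 4.1.3 |
| Grade 3 or above | recorded | recorded | recorded |

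**Reading 1: the specific rule in 4.1.3 governs.** This is the natural reading. Attribution changes the outcome in exactly one row, grade 2 still open at 72 hours.

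**Reading 2: the exception is confined to its own sentence.** The exception clause in 4.1.2 is attached to the grade 3+ sentence and is not repeated for grade 2. Taken literally, the grade 2 sentence captures a persistent bead reaction that 4.1.3 says is collected only from grade 3. The asymmetry goes, but the two sections contradict each other.

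**Is the event recovered elsewhere?**

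- Section 5.2.2 tabulates related grade 2 events at continuing review only if they are unexpected. Section 4.1.3 labels bead allergy as anticipated, so a non-serious grade 2 bead reaction is not recovered there.
- Section 4.1 says that adverse events of any severity are followed for 30 days or until they return to baseline or stabilise. That concerns follow-up. It adds to the inconsistency without settling what is recorded.

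**Can attribution bear this weight?** Beads and contrast arrive in one suspension (10.1, 10.1.2), and Appendix C does not separate the two allergies. A reaction that begins during or after bead delivery therefore has two candidate causes given at the same moment.

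**The case against.** The strongest reply has four parts.

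1. **The bead entry is a concession.** The TAE and ablation lists in 4.1.3 are excluded by default with no grade floor, and they include bleeding, portal vein thrombosis and pancreatitis. Bead allergy is the only listed event brought back in, at grade 3. This stands. A reader might infer that the plan is least sensitive for its own device, and the lists show otherwise. The contrast holds only against unlisted events such as contrast allergy.
2. **Exclusion is a default.** The principal investigator may collect a listed event judged unexpected. This stands as a qualification. However, the override is discretionary and is worded to require nature, severity and frequency together, so it does not secure the record.
3. **Attribution is not hopeless, and patients are selected.** Section 3.2.1 has contrast arteriography before bead delivery, so timing carries some information. Section 9.5 excludes patients with known allergy to the beads or their components. Both points reduce the problem, but neither separates the agents once the mixture is being injected.
4. **The trial is about imaging.** The only objective is imaging characteristics, and the statistical section plans descriptive summaries with no allergy rate. This limits the severity. It does not justify a recording rule that depends on the suspected agent.

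A reader might also infer that three rules disagree, counting 4.3.1. That section refers to 4.1.3 for details and is largely consistent with it. The real tension is between 4.1.2 and 4.1.3. Nor do the documents support an argument that the pretreatment for known contrast allergy in 9.5 pushes reactions below the recording threshold: they say nothing about its effect on grade.

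**Conclusion.** The point holds in a narrow form and is minor. Under the natural reading, and without the override, a grade 2 allergic reaction open at 72 hours is recorded or lost according to which component of a single injection is blamed. Under the literal reading of 4.1.2, the two sections contradict each other. Both readings need the same reconciliation.

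The size is one row of the table. It is tempting to put a probability on missed reactions by assuming a rate for all grade 1 and 2 reactions. That would not measure this defect: grade 1 reactions, and grade 2 reactions resolved by 72 hours, go unrecorded whatever their cause. The documents give no rate for persistent grade 2 reactions, so no count is offered.

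The conclusion rests on two assumptions: that the specific entry in 4.1.3 prevails over the general sentence in 4.1.2, and that contrast allergy, being unlisted, follows the general rule.

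**What to change.** In 4.1.3, replace the grade 3 threshold under the bead heading with a rule that any allergic reaction from the start of bead delivery to the end of the 72-hour toxicity window is recorded whichever agent is suspected. Enter attribution (bead, contrast, anaesthetic, other, undetermined) as a separate field.

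- **Minimum version:** apply the existing grade 2 rule of 4.1.2 to all allergic reactions, alongside grade 3 and above. This alone removes the asymmetry.
- **Fuller version:** record allergic reactions at every grade. This goes beyond the asymmetry and needs a stated exception to the grade 1 rule in 4.1.2.

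In either version, state in 4.1.2 whether the exception clause applies to the grade 2 sentence, and align the toxicity bullet of 4.3.1. Report allergic reactions as n/N by grade, with N the number of patients who received beads, and state the lowest grade captured.

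The cost is wording in three sections and a few more adverse event records, with no added visit or test and no change to clinical management. The downside is slightly more data entry and a possibly less favourable allergy count.

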4.1.4 Follow up of Adverse Events

All adverse events will be followed until they have abated, or until a stable situation has been reached. Depending on the event, follow up may require additional tests or medical procedures as indicated, and / or referral to the general physician or medical specialist.

The investigator will evaluate reported adverse events for determination of seriousness and causal relationship with the treatment or the device.

4.1.5 Device Records

Records or receipt, use, and disposition of the LC Lumi Radiopaque Embolic beads will be kept according to 21CFR 812.140 (a).

- The size, batch number, and expiration date will be recorded for each patient.
- The name of the person who received and used the beads will be documented. Disposal of beads, if unused, will also be recorded as well as the person's name who handled the disposal.
- Any bead deficiency will also be recorded along with the correspondence with the manufacturer.

4.1.6 Handling and storage of data and documents

All individual patient data and records will be collected and maintained on confidential basis and according to the applicable national data protection, privacy, and security laws. Data collected from subjects enrolled in this protocol may be used in submissions to regulatory agencies, and for publications. Summaries of data and information from each patient data form may be used for statistical analysis of the investigation's finding during trial.

Trial data will be recorded in a database during the trial. Each patient will receive a unique study ID. The study investigator shall safeguard a list linking subject names to their ID numbers. Access to the database is restricted to personnel involved in conducting the trial. Final trial data for the report is expected to be in the database within 3 months from completing the last patient's follow-up.

The study investigator will also be responsible for maintaining all correspondence pertaining to the investigation. All shipment, receipt, and disposition of the study device will be kept in the electronic regulatory binder. Also kept in the regulatory binder are signed investigator agreements, study investigators' OSHPD training certificates, and COI records.

4.1.7 Record Retention

The investigator will retain the specified records and reports for up to 2 years after the marketing application is approved for the investigational device.

4.2 DATA SHARING PLANS

4.2.1 Human Data Sharing Plan

What data will be shared?

I will share human data generated in this research for future research as follows:

De-identified data in BTRIS (automatic for activities in the Clinical Center)

De-identified or identified data with approved outside collaborators under appropriate agreements.

How and where will the data be shared?

Data will be shared through:

- An NIH-funded or approved public repository. Insert name or names: clinicaltrials.gov.
- BTRIS (automatic for activities in the Clinical Center)
- Approved outside collaborators under appropriate individual agreements.
- Publication and/or public presentations.

When will the data be shared?

- Before publication.
- At the time of publication or shortly thereafter.

4.3 RESPONSE CRITERIA

4.3.1 Definitions

- Evaluable for bead visibility: All patient imaging will be evaluated for the visibility of the LC LUMI beads using a 3 point scale: 0, definitely not visible; 1, probably visible; and 2, definitely visible as defined the treating interventional radiologists. Other characteristics may be noted such as the radiopacity of the beads, visibility of the beads in the tumor, overall location of beads in relation to the tumor or targeted site.
- Evaluable for toxicity: All patients will be evaluable for toxicity from the time of their treatment with LC LUMI radiopaque beads up to 72 hours post completion of treatment. Grade 3 or greater adverse events, including allergic reactions, collected during this time period, will be followed until resolution. Expected or anticipated adverse events from the research or the study device will not be collected. See Section **4.1.3** for details.
- Evaluable for imaging characteristics: Only those patients who are eligible for the study, have received at least one treatment of TAE, and have had their disease re-evaluated per standard of care imaging will be considered evaluable.

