catheterized for TAE with LC LUMI beads. An attempt will be made to exclude the cystic artery from the embolization distribution. Extrahepatic branch vessels may be prophylactically embolized at the discretion of the Principal Investigator to mitigate the risk of non-target deposition of LC LUMI beads. TAE will continue typically until near-complete flow stasis is observed in the target artery (where no non-target reflux of contrast material into more proximal branches is observed). If significant antegrade flow is observed in the target artery following procedure, additional embolization using LC LUMI beads may typically be added to reach the embolization endpoint. Visibility of the LC LUMI beads will be recorded using a 3 point scale: 0, definitely not visible; 1, probably visible; and 2, definitely visible. A CBCT scan *may* be obtained post LUMI beads injection to evaluate virtual perfusion characteristics of the beads for predictive investigations of their delivery and function.. The catheter will then typically be retracted into the common hepatic artery and completion arteriography will document the degree of target vessel flow stasis and non-target vessel patency.

Thermal ablation therapy may be administered based on the clinical evaluation of the patient and when appropriate will be done according to the manufacturer's instructions for use. After infiltration of the skin (for percutaneous approach) with a local anesthetic, the needle of the chosen system will be directed into the lesion, with image guidance and the needle is confirmed to be in the lesion by imaging. After confirming appropriate positioning, the lesion will be heated typically for 10-15 minutes, according to manufacturer's guidelines. The exposure time may be varied depending on the temperatures achieved and proximity of adjacent anatomy or other patient-specific anatomy or issues. Depending on the size of the lesion to be ablated, multiple locations of the needle as well as multiple ablation cycles will be performed in order to ideally achieve an approximately 1-cm margin of ablated tissue around the lesion or target volume. Adequacy of ablation will be followed by ultrasound throughout the procedure, when possible. Depending on the size of the lesions and the time required to complete the ablation, multiple lesions may be treated, often as staged procedures.

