7.0 STATISTICAL CONSIDERATIONS

This is a proof of concept/feasibility study with a small number of evaluable patients and data points. Data collected will not be sufficient to provide meaningful statistical analysis.

Sample size was derived from historical experience with pilot feasibility observational studies, where a population of 20-30 evaluable patients should provide initial information to begin to characterize the imaging features of the approach, which is the main goal. This should allow for adequate slight variations in dosages and anatomy to inform such a pilot study. The precise characterization of the imaging features will require a much larger future study, but this pilot study outcomes and imaging features could be used to power future studies, depending upon the primary aims. No statistical analysis is required to power this trial, as it is a pilot feasibility study, and the outcomes related to imaging features will not be statistically analyzed, other than simple descriptive statistics. Descriptive statistics will be provided in summary tables.

- Categorical variables will be summarised using frequency distribution: number of observations (N) and percentages (%).
- Continuous variables will be summarized using standard quantitative statistics:
 - number of observations (N),
 - mean, standard deviation (STD),
 - median and
 - range (minimum and maximum observed values).

When relevant, the 95% confidence intervals (CI) will also be displayed.

For instance, qualitative analyses may be done to compare virtual and actual perfusion characteristics (such as overlap) of LUMI beads using CBCT before, during, and after LUMI beads injection.

If fewer than 20 evaluable patients are enrolled, then the variety of imaging features seen may be limited. Using fewer than 20 evaluable patients could start to substantially compromise the ability of the study to provide the necessary rationale for further work in refining and developing the clinical use of this approach. Since the emphasis is that this is a PILOT study, this recommended study size of N=20 EVALUABLE patients seem to be a good compromise.

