Lastly, assuming that possibly up to 33% of recruited patients may turn out to either be ineligible or that their data will be inevaluable, a total of N=30 patients will need to be recruited to ensure having (roughly) 20 evaluable patients. If a patient's follow-up imaging is not available but their procedural data is adequate they will be considered evaluable. Inevaluable patients are defined

Abbreviated Title: RFA + TACE with RO Beads

Version Date: 04/13/2018

as patients whose data cannot be reliably recorded in terms that satisfy the primary endpoint. This could occur if the data cannot be graded in terms of visibility due to technical issues such as patient motion or small doses of beads used in a small volume of tissue.

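### Bead location outside the target is optional to record and has no named summary, and the adverse event rules disagree on whether late or exempted non-target harm is collected

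*Combined protocol and SAP*

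**What the plan says.** **Imaging.** The only objective (1.1.1) concerns the imaging characteristics of the beads, including a qualitative comparison of virtual and actual bead perfusion. Section 4.3.1 has all patient imaging graded 0/1/2 for bead visibility (see also 3.2.1 and 4.1.2). It then adds: "Other characteristics may be noted such as the radiopacity of the beads, visibility of the beads in the tumor, overall location of beads" relative to the tumor or target. Related provisions:

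- 3.2.1: after embolization the catheter is typically withdrawn and "completion arteriography will document the degree of target vessel flow stasis and non-target vessel patency". The same section allows deliberate occlusion of side branches: "Extrahepatic branch vessels may be prophylactically embolized at the discretion of the Principal Investigator".
- 3.2.3: a CT is to be obtained within 2 months of treatment to evaluate bead perfusion.
- 4.1.2: procedural and follow-up images are archived.
- 7.0: imaging outcomes get simple descriptive statistics, with 95% confidence intervals where relevant. The spatial comparison is permissive: "qualitative analyses may be done to compare virtual and actual perfusion characteristics (such as overlap) of LUMI beads". If a patient's "follow-up imaging is not available but their procedural data is adequate they will be considered evaluable".
- 9.5 lists misembolization as a harm and its immediate visualization as a mitigation. 10.1 gives detection of non-target embolization as an expected benefit of the bead.

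**Adverse events.** Section 4.1.2 collects "Any grade 3 events and higher occurring up to 72 hours post treatment", plus grade 2 events unresolved at that point. Under 4.1.3, listed anticipated events "will not be collected unless the nature, severity, and frequency are deemed by the PI as unexpected for this patient population". The embolization list includes acute cholecystitis and "Acute pancreatitis or elevation of amylase and lipase". The risk table in 9.5 dates abdominal visceral injury from non-target embolization at 1-2 weeks.

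**The concern.** Where the beads went is itself an imaging characteristic, so it belongs to the existing objective and needs no new endpoint. A patient with clearly visible stray beads and a patient with perfect targeting can both score 2 on the required scale. When a location note is optional, a blank does not distinguish no stray beads from not looked for. Nor does the plan separate stray beads from deliberate branch embolization.

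On the safety side, the harm that stray beads cause is expected after routine collection has ended, and two of its possible forms are exempt. Staff who follow different sections could reach different decisions about the same event. Section 5.4.1 bases decisions on continued enrollment on earlier patients' toxicity, so the inconsistency matters during the trial as well as at its end.

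**Working it through.** **1. Denominator.** The plan's recruitment figure reproduces: 20 / (1 − 0.33) = 29.85, rounded up to 30. A location count would therefore rest on about 20 evaluable patients, and at most 30 treated.

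**2. Does another imaging item supply the location count?**

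- Visibility grade: required, but carries no location.
- Completion arteriography: documents vessel patency, not bead position; 3.2.1 describes it as typical practice, and 7.0 names no summary of it.
- Virtual/actual overlap: optional in 7.0. Poor overlap can mean beads missing from the predicted territory or beads beyond it, so it does not count patients with stray beads.
- CT within 2 months: a source of images, but no off-target reading is specified, and 7.0 lets a patient without it count as evaluable.

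**3. Timing.** 72 hours = day 3; 1-2 weeks = days 7 to 14. Collection closes 7 − 3 = 4 to 14 − 3 = 11 days before the expected injury. If section 4.1 is read as a 30-day collection rule, the whole period is covered with 30 − 14 = 16 days to spare. For new non-serious events in that period, the two readings capture none or all.

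**4. Exemptions.** The embolization list in 4.1.3 has 15 entries. The documents tie 2 of them to non-target vessels: pancreatitis (given under non-target embolization in the Appendix C instructions for use) and cholecystitis (3.2.1 tries to keep the cystic artery out of the embolized area). Gastric ulceration is not exempt.

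**5. The rules applied to three hypothetical non-serious events.**

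| Event | 4.1.2 and 4.1.3 | 4.1, read as 30 days | 5.2.2, continuing review |
|---|---|---|---|
| Gastric ulcer, grade 3, day 10 | Not collected | Covered | Tabulated if related |
| Gastric ulcer, grade 2, day 10 | Not collected | Covered | Only if related and unexpected |
| Pancreatitis, grade 3, day 2 | Exempt unless the principal investigator deems it unexpected | Covered on its face | Tabulated if related |

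The calendar in 3.3 also marks adverse events during follow-up, but its footnote refers to 4.1.4, which sets neither a window nor a grade. Section 5.2.2 sets no time limit, but nothing says how an event that 4.1.2 or 4.1.3 leaves out would reach its table.

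**6. What a complete count could show.** Exact two-sided 95% upper limit for 0 of n = 1 − 0.025^(1/n): 30.8% for n = 10, 21.8% for n = 15, 16.8% for n = 20 and 11.6% for n = 30. For 2 of 20 (10%) the Clopper-Pearson interval is 1.2% to 31.7%. These support description only.

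**7. Illustration, not an estimate.** The documents give neither a deposition rate nor a note-completion rate. Assume 2 true cases and notes made for a fraction r of patients, independently of what is seen. The chance that neither case is noted is (1 − r)²: 56%, 25% and 6% for r = 25%, 50% and 75%.

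**The case against.** The case on the other side has force in five places.

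- **The information is not lost.** Images are kept (4.1.2), the objective and 3.2.3 already call for a bead perfusion evaluation, and 7.0 would tabulate any categorical item recorded. A reader might infer that the trial cannot establish where the beads went; the documents do not support that. What is missing is a required item with a definition. The case report forms are not in the file, so this point concerns the protocol text only.
- **Late harm is not simply dropped.** A reader might infer that everything after 72 hours goes uncaptured. That is too strong. Section 5.2.2 requires related grade 3-4 events and all serious events to be tabulated, 5.1.2 counts hospitalization as serious, and 5.2.1 and 5.3 cover deaths and unanticipated problems. Section 4.1 treats serious events after 30 days separately, which suggests 30 days as the general boundary. Many severe visceral injuries would come through these routes. What stands is that the collection rules feeding them conflict.
- **The miss probabilities do not describe this trial.** This stands in full. A radiologist who sees misembolization has more reason to note it, so they are probably too high, and the conclusion does not use them.
- **A careless location item would create false positives.** The beads are non-resorbable, and retreatment and staged lobes are expected (3.2, 3.2.1), so beads correctly placed at one session would look out of place at another. This stands, and the fix allows for it.
- **It is a small descriptive pilot, and a zero count would be weak evidence.** True, but this argues against inference, not against recording an observation that falls within the objective.

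**Conclusion.** The point holds as a gap in required recording and an inconsistency in event collection. It does not threaten the validity of the trial. Bead location is optional and no off-target count is named, so any later figure would come from an unplanned reading without a set definition or a known number of assessable patients. The collection rules do not match the stated 1-2 week timing of non-target visceral injury, and they conflict with 3.3, 4.1 and 5.2.2.

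The affected material is mainly silent deposition and late or exempted events that are not serious. For related grade 3-4 events the reporting duty exists but the collection step is not assured. How often any of this would occur cannot be derived from the documents. The timing result assumes that 1-2 weeks means days 7 to 14 and that 4.1.2 governs which events are collected. The change is worth making because it costs little.

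**What to change.** 1. **Section 4.3.1.** Make bead location a required item for each embolization session, read from images already obtained: newly deposited beads outside that session's intended territory (yes, no or not assessable), with site, modality and date. Define outside as extrahepatic, or hepatic but beyond the catheterized territory; beads in non-tumor liver within that territory do not count. Compare with pre-session images and allow for the territories of all sessions before the scan, so that staged or repeat treatment is not counted; use not assessable where this cannot be done. Record deliberate prophylactic branch embolization separately. Mark a finding seen only on same-session images as suspected, because the beads are injected in contrast agent (10.1.2), and as confirmed if it persists on a later CT.
2. **Section 7.0.** Within the existing descriptive plan, report the number and percentage of assessable treated patients with any yes, the exact 95% confidence interval, the number not assessable, and how many had the later CT.
3. **Sections 4.1.2 to 4.1.4, with the toxicity definition in 4.3.1.** For all treated patients, collect pancreatitis, cholecystitis, gastric or duodenal ulceration and other visceral injury through 30 days after each embolization, regardless of the 4.1.3 exemption, from the clinical record. Include grade 3 or higher and unresolved grade 2 (unresolved at 72 hours for early events, at record review for later ones). State the window in 4.1.4, so that the calendar footnote points to a rule and 3.3, 4.1, 4.1.2 and 5.2.2 agree.

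**Cost.** No new scan or visit. It adds one location item per session, one tick for prophylactic embolization, a short table, and chart review of a few event types for up to 30 patients. Treating radiologists would still read their own procedures, the denominator would depend on clinically driven imaging, and late capture would be incomplete because no 2-week visit is scheduled (3.2.3).
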